4. **Importance of preeclampsia in the U.S.** Preeclampsia, a potentially fatal pregnancy condition characterized by high blood pressure, is estimated to complicate 3 percent to 6 percent of all pregnancies¹⁻². The rate of preeclampsia in the U.S. has increased 25 percent in the past two decades²². Preeclampsia is a leading cause of maternal and infant illness and death^{1;4-5;8}. Non-Hispanic Black women carry a 3- to 4 fold greater risk of dying from pregnancy-related preeclampsia^{3;12;20}. For example, preeclampsia is associated with 20-30% preterm births and 15% low birth weight^{1;5}. Moreover, a significant number of women who get preeclampsia are at increased risk for cardiovascular disease after pregnancy and throughout their lives.^{1;8;23}

C. Rationale

1. We posit that the implementation of HGPC-T for continuous high blood pressure monitoring is a critical step in closing disparities in preeclampsia. This research has the potential to reduce preeclampsia disparities by considering system change in the delivery of maternal care, continuous monitoring of blood pressure, reducing barriers in transportation and time off from work, improving patient hypertension education, and improving social support and peer-to-peer learning.
2. This research has the potential to reduce preeclampsia disparities by considering system change in the delivery of maternal care continuous monitoring of blood pressure, reducing barriers in transportation and time off from work, improving patient hypertension education, and improving social support and peer-to-peer learning.

3. The study may reduce preeclampsia and improve management of pregnancy-related hypertension.

II. Research Plan and Design

- A. Study Objectives:** The objective is to enhance the Centering GPC intervention with telehealth and take care of your blood pressure (TCYB) intervention for hypertension monitoring.
- B. Study Type and Design:** We will use REDCap software to assign 72 women in a 2:1 randomization scheme in variable block sizes to, respectively, Centering -Health, Empowerment, Reproduction (HER) or usual doula care. You will have a 2 out of 3 chance to participate in the intervention. "Group assignments are random, like flipping a coin or rolling the dice."
- i. Group 1-Non-Intervention
 1. Receive usual doula prenatal care including regular prenatal care visits.
 2. Participants will complete a baseline survey, antepartum study survey, and for postpartum survey

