 - ii. Group 2- Centering HER intervention
 1. Once selected for the study, you will participate in usual prenatal care visits with an OBGYN, 7 doula led virtual intervention sessions visits with an OBGYN fellow oversight.
 2. The 7 virtual meeting will be an hour and a half and led by a doula. A research staff member will be present to help with the coordination of the virtual intervention.
 3. You will receive 7 virtual visits with a group of women participating in the study
 4. Each telehealth/virtual visit will discuss blood pressure/hypertension, blood pressure, nutrition, weight management, exercise, and risk factors for hypertension.
 5. Participants will receive a Bluetooth blood pressure cuff, apple watch (if applicable), and doula tailored care to take your blood pressure and weight at home.
 6. Self-report blood pressure and weight
 7. Participants will complete a baseline survey, antepartum study survey, and for postpartum survey.
 8. Keep a medication log if applicable

Intervention Table

Feature	Group 1: Non-Intervention (Usual Doula Care)	Group 2: Centering HER Intervention
Prenatal Care	Standard doula support + routine prenatal care with OB/GYN	Routine prenatal care + 7 virtual doula-led intervention sessions with OB/GYN fellow oversight

Feature	Group 1: Non-Intervention (Usual Doula Care)	Group 2: Centering HER Intervention
Doula Involvement	Yes – access to traditional doula support during prenatal visits	Yes – virtual group doula-led health education and coaching
Group Sessions	None	7 virtual group sessions (90 min each) with other pregnant participants
Session Topics	Not applicable	Hypertension, blood pressure, nutrition, exercise, risk factors
Technology Provided	None	Bluetooth BP cuff, Apple Watch (if applicable)
Self-Monitoring	No	Participants self-monitor and report blood pressure and weight
Survey Completion	Baseline, antepartum, and postpartum surveys	Baseline, antepartum, and postpartum surveys
Medication Tracking	No	Keep medication log (if applicable)
Research Staff Involvement	Minimal such as surveys, reported blood pressure	Yes – staff assist with coordinating virtual sessions

Timeline

Month	Activities	Milestones / Notes
Month 0-December	Study Launch + IRB Finalization– Finalize recruitment materials– Train staff + doulas– Set up data tracking and virtual platforms	IRB approval confirmed; staff orientation completed

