Month 1-February	Recruitment Begins– Begin enrolling both groups (target ~5 per group)– Distribute flyers, contact clinics, etc.	First 10 participants enrolled (5 intervention, 5 control)
Month 2-3	Continue Recruitment + Begin Intervention– Enroll next 10 participants– Begin Group 1 surveys– Intervention Group 1 starts Session 1	~50% enrollment milestone reached
Month 4	Recruit Final Cohort– Enroll remaining 36 participants– Distribute Apple Watches and BP cuffs– Start Sessions 1–2 for final intervention groups	72 participants fully enrolled (36 per group)
Month 5	Midpoint Engagement– Intervention: Sessions 3–4 (Blood Pressure, Nutrition)– Track self-monitoring data– Group 1 completes mid-surveys	Monitor adherence and troubleshoot any tech issues
Month 6	Continue Sessions + Surveys– Sessions 5–6: Physical activity, medication awareness– Group 2 logs vitals– Group 1 continues routine care + surveys	Most intervention participants complete 75% of sessions
Month 7	Final Session + Postpartum Planning– Session 7: Doula support, preparing for delivery– Collect	Sessions concluded for intervention group

Month	Activities	Milestones / Notes
	antepartum surveys– Encourage postpartum follow-up prep	
Month 8	Final Data Collection + Postpartum Surveys– Collect postpartum survey from both groups– Finalize weight/BP logs– Export and clean dataset	Study concludes; prepare for analysis and reporting

C. Sample size, statistical methods, and power calculation

1. Data will be checked for errors, inconsistencies, and missing values. Descriptive statistics (e.g., mean and standard deviation for continuous variables and number and percent for categorical variables) will be presented for all demographic variables, predictors of interest, and outcomes. Chi-square and 2-sample t-tests will be used to compare the outcomes among demographic groups and between different treatments.
2. The participants will receive education on nutrition and exercise, will be asked to monitor their blood pressure daily using blood pressure cuffs, and will receive the standard of care of 81mg of aspirin per day (if applicable).
3. This is a pilot project, so there is no power calculation for the project. The total number of participants is 72.

D. Subject Criteria (See Vulnerable Populations appendix, if applicable):

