Appendix E. Measures and Instruments Packet (Inventory)

Instrument / Data Source	Purpose	Timepoints	Notes / Storage
Baseline Survey (REDCap)	Demographics, baseline health behaviors/knowledge, baseline outcomes per study measures table	Baseline (<13 weeks)	Store in REDCap; authorized versions in regulatory binder
Antepartum Survey (REDCap)	Follow-up outcomes and process measures	Late pregnancy / last prenatal visit before delivery	Store in REDCap
Postpartum Survey (REDCap)	Postpartum outcomes and acceptability	Postpartum	Store in REDCap
Home BP and Weight Log (device-supported)	Daily/regular monitoring	Throughout participation	Self-report; Bluetooth cuff/Apple Watch (if applicable)
Medication Log (if applicable)	Aspirin and/or antihypertensive adherence tracking	Throughout participation	Self-report; may be verified by doula if built into workflow
EHR Abstraction	Clinical outcomes including blood pressure, prenatal care utilization, delivery outcomes (as defined)	Ongoing / postpartum	Minimum necessary data; stored on p:protecteddata drive

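### The Timeline gives control women surveys that the intervention arm does not get, and does not secure a baseline survey before open-label allocation

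*Protocol*

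**What the plan says.** **Survey content by arm.** The Group 1 and Group 2 lists in Section II.B each name a baseline, an antepartum and a postpartum survey. The Survey Completion row of the Intervention Table has the same entry in both columns: "Baseline, antepartum, and postpartum surveys". Section III.G pays for these three and no others. Appendix E inventories the same three and sets the first at "Baseline (<13 weeks" of gestation, which is also the enrolment limit in the synopsis.

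**The Timeline (Section II.B).** The survey-related entries run as follows:
- Month 1: "First 10 participants enrolled (5 intervention, 5 control".
- Month 2-3: "Begin Group 1 surveys", followed at once by "Intervention Group 1 starts Session 1".
- Month 5: "Group 1 completes mid-surveys". The intervention entry lists sessions and tracking of self-monitoring.
- Month 6: "Group 1 continues routine care + surveys". Group 2 is shown as logging vital signs.
- Month 7: antepartum surveys, not limited to one arm.
- Month 8: postpartum surveys in both groups.

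**Allocation.** Section II.B uses REDCap to "assign 72 women in a 2:1 randomization scheme in variable block sizes". The synopsis calls the trial open-label. The visible text does not say whether the baseline survey comes before or after allocation.

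**The concern.** There are two problems, and the first is the firmer.

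First, staff who follow the Timeline would survey control women on an occasion when intervention women are not surveyed. In a randomised comparison the assessment schedule should be the same in both arms. Appendix E assigns health behaviours and knowledge to the baseline survey and follow-up outcomes and process measures to the antepartum one. Section V.D plans a publication on health behaviours. Repeated questioning in one arm only can influence later answers or conduct in that arm, and data from a control-only mid-survey have nothing to be compared with.

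Second, the baseline survey is meant to hold baseline outcomes, behaviours and knowledge. If a woman completes it knowing her arm, or around her first group session, her answers may already reflect the allocation. A baseline lost in this way cannot be collected again. The protocol should therefore fix the order, and the only month-by-month schedule in it points the wrong way if read literally.

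**Working it through.** **Check 1: number of surveys per arm.**

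| Source | Control | Intervention |
|---|---|---|
| II.B group lists | 3 | 3 |
| Intervention Table | 3 | 3 |
| III.G Payment | 3 paid | 3 paid |
| Appendix E | 3 listed | 3 listed |
| Timeline, Month 5 | mid-survey | none shown |
| Timeline, Month 6 | surveys, type and number not given | none shown |

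In the Month 5 and Month 6 rows Group 1 is set against the intervention sessions and against Group 2, so it is the control arm. The Month 5 mid-survey is one extra occasion. The Month 6 entry adds zero or more, because it may be a new occasion or a continuation. The excess in controls is therefore at least 1 + 0 = 1.

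**Check 2: time from known arm to start of surveys.** Let Month m run from m − 1 to m.
- Month 1 enrolment falls between 0 and 1.
- A start in Month 2-3 falls between 1 and 3.
- Shortest gap: 1 − 1 = 0 months. Longest gap: 3 − 0 = 3 months.
- From mid-Month 1 (0.5) to mid-Month 2 (1.5) or mid-Month 3 (2.5): 1.5 − 0.5 = 1 month, or 2.5 − 0.5 = 2 months.

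**Check 3: how many women the Timeline shows with an arm before surveys begin.** It shows 10 of 72 = 13.9%. If the Month 2-3 entry concerns controls only, it shows 5 women. Under 2:1 allocation there are 72 × 1/3 = 24 controls, so 5/24 = 20.8%. Under the Timeline's own figure of 36 per group, 5/36 = 13.9%. No delay is shown for women enrolled later.

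**Check 4: would a survey begun then still meet the limit of less than 13 weeks?** Suppose that it is the baseline survey, and take 4.345 weeks to a month. A woman misses the window if her gestation at enrolment is at or above 13 − 4.345 × gap:
- gap 0 months: 13 − 0 = 13 weeks, so nobody misses it;
- gap 1 month: 13 − 4.345 = 8.7 weeks;
- gap 2 months: 13 − 8.69 = 4.3 weeks;
- gap 3 months: 13 − 13.035 is below zero, so everybody misses it.

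The range runs from none to all, and the protocol gives no distribution of gestation at enrolment that would narrow it.

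**The case against.** The strongest reply is that the Timeline is a project calendar, not a participant-level schedule, and an unreliable one. Its enrolment entries add to 10 + 10 + 36 = 56, not 72. It describes 20/72 = 28% as about half. Its 36 per group conflicts with 2:1, which gives 48 and 24. Reading individual survey timing from its row order asks too much of it. That stands as a limit on what the Timeline proves about practice. It does not excuse the contradiction, because it is the only month-by-month survey schedule in the text and staff may work from it.

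A reader might infer several stronger things that the document does not support:
- **That the baseline is in fact collected after randomisation.** The Month 2-3 entry names no survey. Its group label is ambiguous, since the next item applies the same number to an intervention cohort. Appendix E ties the baseline survey to the enrolment window.
- **That the gap is at least a month.** It can be close to zero.
- **That most of the first women would be surveyed outside the window.** This needs data on gestation at enrolment, which are not given.
- **That controls complete five surveys against three.** This counts Month 6 as a separate new occasion, which the text does not say.

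Two further points have weight. The attachments list names a Schedule of Events that is not in the text at hand and may settle the order; if it does, the Timeline still needs to agree with it. Also, Section V names blood pressure as the outcome, drawn partly from records and home logs, and its t-tests and chi-square tests use no baseline adjustment. What is at stake is therefore mainly the survey-based comparisons. That one extra survey would change behaviour is a possibility, not something the document shows.

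**Conclusion.** The contradiction over surveys is established. The Timeline gives the control arm at least one survey occasion that the intervention arm lacks, and four other places in the protocol give both arms the same three. This rests only on reading Group 1 in Months 5 and 6 as the control arm, which the contrast in those rows makes plain.

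The point about the baseline holds in a limited form: the protocol does not secure a baseline survey before open-label allocation. Read literally, surveys begin 0 to about 3 months after the first 10 women are shown with an arm. Meeting the limit of less than 13 weeks does not cure this, because a woman can be allocated and then surveyed within that window. Whether any baseline survey is actually late cannot be determined from the document.

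The likely effect is on the survey outcomes and on the description of the arms at baseline. Its size cannot be computed from what is given. The point deserves correction because the remedy is cheap and a compromised baseline cannot be recovered.

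**What to change.** 1. Reconcile the Timeline with the Intervention Table and Appendix E so that both arms complete the same surveys at the same timepoints. Either remove the control-only mid-survey and Month 6 surveys, or give them to both arms and add the instrument to Appendix E and the payment section.
2. Move the start of surveys in the Timeline to enrolment, and use arm names there, not numbers that can also mean a cohort.
3. State that the baseline survey is completed after consent, at less than 13 weeks, and that REDCap releases the allocation only once it has been submitted.

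The cost is an edit to one table, one sentence on order and one REDCap rule. The downside is that allocation waits until one survey is complete. If mid-surveys are kept for both arms, there is also the burden of that survey in the intervention arm.

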Official Study Title

Improving Prenatal Care to Reduce Early Onset Preeclampsia in Low-Income Black Women in Kansas

ClinicalTrials.gov Identifier

NCT Number: *Pending registration at ClinicalTrials.gov*

Principal Investigator

[name], PhD

University of Kansas Medical Center (KUMC)

Study Sponsor

National Institutes of Health (NIH)

IRB Protocol Number

STUDY00160319

Version Date of This Protocol Document

February 9, 2026

Site Name: University of Kansas Medical Center

Kansas City, Kansas

University of Kansas Medical Center
RESEARCH PROTOCOL INVOLVING HUMAN SUBJECTS
TEMPLATE WITH GUIDANCE

Version date: 02.09.2026

Principal Investigator: [name]

Study Title: *Improving Prenatal Care to Reduce Early Onset Preeclampsia in Low-Income Black Women in Kansas*

[name], [name], [name], [name], [name]

1. Protocol Synopsis

Study Design

Prospective, two-arm randomized controlled trial; parallel assignment; open-label (behavioral/telehealth intervention).

Randomization: 2:1 allocation using REDCap with variable block sizes.

Framework: Practical, Robust Implementation, and Sustainability Model (PRISM) to guide implementation, adoption, effectiveness, maintenance, and pragmatism evaluation.

Population

Pregnant participants, age ≥ 18 years.

English or Spanish speaking.

Less than 13 weeks gestation at enrollment.

Moderate or high risk for preeclampsia per USPSTF criteria.

Intervention (Arm 2)

Centering HER (HGPC-T): routine prenatal care plus 7 doula-led virtual group sessions (90 minutes each) with OB/GYN fellow oversight.

Participants receive Bluetooth BP cuff and (if applicable) Apple Watch; self-monitor and self-report blood pressure and weight; complete surveys and medication log (if applicable).

Comparator (Arm 1)

Usual doula prenatal care and routine prenatal care visits with OB/GYN; completes study surveys.

Primary/Key Outcomes (as stated in source protocol)

Blood pressure rates; hypertension monitoring and aspirin compliance (# of women monitoring BP and aspirin compliance).

Feasibility, acceptability, and contextual factors required for implementation.

Duration

Enrollment at <13 weeks gestation through postpartum survey completion (baseline, antepartum, and postpartum surveys).

Data Sources

REDCap surveys (baseline, antepartum, postpartum).

Self-reported BP/weight (device-supported); medication log (if applicable).

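### Allocation is fixed at 2:1 in the Synopsis and II.B, but the Timeline plans 36 women per arm, and its monthly counts total 56 rather than 72

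*Protocol*

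**What the plan says.** The Protocol Synopsis (Study Design) gives "Randomization: 2:1 allocation using REDCap with variable block sizes". Section II.B (Study Type and Design) repeats the ratio, gives the total and names the order of the arms: the plan is to "assign 72 women in a 2:1 randomization scheme in variable block sizes to, respectively, Centering -Health, Empowerment, Reproduction (HER) or usual doula care". The participant wording that follows agrees: "You will have a 2 out of 3 chance to participate in the intervention". Section II.C confirms a total of 72 and says that, as a pilot, the study has no power calculation.

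The Timeline table, placed after the Intervention Table in II.B, reads differently:

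- **Month 1:** a target of about five per group, with the milestone "First 10 participants enrolled (5 intervention, 5 control".
- **Months 2-3:** "Enroll next 10 participants", with a milestone of roughly half of enrolment.
- **Month 4:** 36 women said to remain, with the milestone "72 participants fully enrolled (36 per group".

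**The concern.** The allocation ratio is a basic design parameter, and the REDCap allocation table can hold only one. The design text sets 2:1, while the Timeline sets equal arms both at the start and at the end of recruitment. An analysis plan cannot settle this, because the ratio, the arm targets and the monthly counts are all fixed in the protocol and disagree there.

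Three things depend on the answer. The loaded table must match the odds given to participants. The virtual groups must be sized for either 36 or 48 women. Recruitment must be tracked against arm totals that the randomisation can actually reach. If staff treated 36 per arm as a goal while REDCap assigned 2:1, the milestone could not be met by following the assignments.

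Separately, the monthly entries do not lead to the total that the same table reports.

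**Working it through.** **Inputs.** Total 72 (II.B, II.C, Month 4 milestone). Ratio 2:1, intervention to control (Synopsis, II.B). Arm targets 5:5 and 36:36, and monthly entries 10, 10 and 36 (Timeline). The protocol has no power figure to reproduce.

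**1. Arm sizes under the stated ratio.** Intervention 72 × 2/3 = 48; control 72 × 1/3 = 24. The Timeline's 36 and 36 is 72 × 1/2. The difference is 48 − 36 = 12 in one arm and 36 − 24 = 12 in the other. The 48:24 split is derived; the protocol does not print it.

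**2. Could 36:36 arise by chance under 2:1?**

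- *Blocked, one list (no stratification is stated).* Complete blocks give exactly one third controls, so any excess must come from one unfinished block. If r women of that block have been assigned and c of them are controls, the excess over one third is c − r/3. Reaching 36 controls needs an excess of 36 − 24 = 12. Since c cannot exceed r, 2r/3 ≥ 12, so r ≥ 18. Then c = 12 + r/3 ≥ 18, and a 2:1 block with at least 18 controls has at least 3 × 18 = 54 places. No realistic block length in a 72-woman trial allows this.
- *Simple randomisation, which is looser than the plan.* P(36 or more controls of 72, each with probability 1/3) ≈ 0.0025.
- *Total needed for 36 controls at 2:1.* 36 × 3 = 108 women, not 72.

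**3. The Month 1 figure.** At 2:1 the first 10 would split on average 6.7 to 3.3. A 5:5 split has probability C(10,5) × (1/3)^5 × (2/3)^5 = 0.137 under simple randomisation, so it is unremarkable as an outcome. The Timeline sets it in advance as a target, however, and as a target it matches 1:1 and not 2:1.

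**4. Monthly counts.**

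| Reading of the Months 2-3 entry | Sum | Enrolled before Month 4, of 72 |
|---|---|---|
| 10 in all (literal) | 10 + 10 + 36 = 56 | 20 = 28% |
| 10 per month, or 10 per group | 10 + 20 + 36 = 66 | 30 = 42% |
| 10 per group per month | 10 + 40 + 36 = 86 | 50 = 69% |
| 26 in all | 10 + 26 + 36 = 72 | 36 = 50% |

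No reading of the printed entry gives 72. The literal sum is 72 − 56 = 16 short. The half-way milestone, the 36 remaining and the total of 72 agree with one another, so the Months 2-3 entry looks like the odd one out.

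**5. Precision.** With equal variances, the ratio of standard errors for a between-arm difference is √[(1/48 + 1/24) / (1/36 + 1/36)] = √(0.0625 / 0.0556) = √1.125 = 1.061, about 6% larger at 48:24.

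**6. Intervention places.** 48 against 36 is 12 more, or +33%. At the $25 per session in III.G and seven sessions, that is 12 × 7 × $25 = $2,100 in session payments if all sessions are attended.

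**The case against.** The best defence is that the governing ratio is clear enough. The Synopsis, II.B and the participant wording all say 2:1, REDCap makes the assignments, and the Timeline is only a planning table. It has no rule for closing an arm, so the likeliest result is a missed milestone. This stands as a reason to treat the Timeline as the outlier and 2:1 as the presumptive ratio. It does not make the 36-per-arm milestone correct, and the sponsor still has to confirm which was meant.

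A reader might infer more than the text supports:

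- **That the coin image shows a 1:1 plan.** The sentence is "Group assignments are random, like flipping a coin or rolling the dice". It is a lay picture of chance, a die does not imply equal odds, and the exact odds stand immediately before it.
- **That 16 women are missing from planned enrolment.** Every stated total is 72; only the monthly entries fail to add up.
- **That 26 is the only possible repair.** It is forced only if Month 1 stays at 10. Any Month 1 and Months 2-3 counts adding to 36 would fit. If both tens are right, the remaining number would be 72 − 20 = 52 and the half-way milestone would be wrong.
- **That cuff numbers rise by a third.** The Intervention Table gives controls no technology, but the Study Procedures in II.E give every participant a cuff and scale. On that reading the cuff count does not depend on the ratio.
- **That allocation will be steered, or an arm closed early.** Nothing in the protocol instructs this. It is a risk only if staff work to the Timeline's arm totals.
- **That power is lost.** No power or precision is claimed, so the 6% undoes no stated figure.

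**Conclusion.** The contradiction is real and stands in current text. The design sections imply 48:24 and the Timeline states 36:36, a difference of 12 women in each arm that chance under the stated scheme does not explain. This rests on a total of 72, a single unstratified randomisation list, and blocks shorter than 54. It should be corrected because the allocation table, the odds told to participants and the session capacity all depend on it. The effect on precision is minor.

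The monthly counts (56 against 72, and 28% against about half) are a secondary planning error in the same table. On their own they would be clerical.

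**What to change.** State one ratio throughout the protocol and check it against the REDCap allocation table before it is used or, if enrolment has begun, against the table already loaded.

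- **If 2:1 is confirmed,** as the Synopsis, II.B and the participant wording indicate: change the Month 4 milestone to about 48 Centering HER and 24 usual doula care. Delete the Month 1 per-arm targets and milestone split, so that arm counts simply follow the randomisation.
- **If 1:1 was intended:** change the Synopsis, II.B and the two-in-three statement to participants instead.
- **In either case:** correct the monthly counts so that they total 72. One option for the sponsor to confirm is 26 women in Months 2-3 with Month 1 kept at 10, which fits both the half-way milestone and the 36 remaining.

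The cost is a few wording changes and one check of the allocation table. Under 2:1 the team must plan for 12 more intervention participants than the Timeline shows. The 26-woman option also states a faster recruitment pace for Months 2-3.

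### The Month 8 close contradicts follow-up through the postpartum survey: at least half the sample enrols in Month 4 and is at most 34.6 weeks pregnant when the study ends

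*Protocol*

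**What the plan says.** The Protocol Synopsis sets the population criterion "Less than 13 weeks gestation at enrollment", and section II.D.1 repeats it. The Synopsis entry on duration has each participant followed from that enrolment until the postpartum survey is done.

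The only operational schedule is the timeline table in section II.B; section II.E.5 marks its timeline item as not applicable. The table runs as follows:

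- "Month 1-February": recruitment starts, with the milestone "First 10 participants enrolled (5 intervention, 5 control)".
- Months 2–3: "Enroll next 10 participants", with a milestone of roughly half the sample enrolled.
- Month 4: "Enroll remaining 36 participants", with a milestone of 72 enrolled.
- Month 7: antepartum surveys are collected.
- Month 8: "Collect postpartum survey from both groups", finalise the weight and blood pressure logs, export and clean the data. The milestone is "Study concludes; prepare for analysis and reporting".

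Appendix E places the antepartum survey at "Late pregnancy / last prenatal visit before delivery". It places the postpartum survey after delivery, and abstraction of delivery outcomes from the health record as ongoing and postpartum. Section III.G pays for the antepartum surveys at the last visit before delivery. Nothing in the protocol describes follow-up after Month 8.

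**The concern.** Month 4 to Month 8 is five months at most. A woman who enters before 13 weeks cannot reach term in five months, so she cannot have a term delivery or a survey after one. The timeline and the stated per-participant follow-up cannot both be carried out.

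Aims 2 and 3 ask whether the intervention reduces preeclampsia, and Appendix E collects acceptability, part of Aim 1, in the postpartum survey. If the table is followed, those data are cut short for a large part of the sample, and the loss is not random. A Month 4 enrollee can have delivery or postpartum data at closure only if her pregnancy ended early.

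**Working it through.** **Enrolment count.** The table's stated total is 72. Its monthly counts give 10 + 10 + 36 = 56, so the total does not reproduce. The share enrolled in Month 4 depends on which entry is right:

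- Month 4 count and total both as stated: 36/72 = 50%, which agrees with the half-enrolled milestone for Months 2–3.
- Earlier counts and total as stated: (72 − 20)/72 = 52/72 = 72%.
- Monthly counts as stated: 36/56 = 64%.

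Every reading gives at least half.

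**Gestation at closure.** Inputs: maximum gestation at entry, 12 weeks 6 days = 12.86 weeks (Synopsis); closure at the end of Month 8 (timeline); one month = 365.25/12/7 = 4.348 weeks. The best case is enrolment on the first day of the month:

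maximum gestation at end of Month 8 = 12.86 + (9 − enrolment month) × 4.348

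| Enrolment month | Calculation | Maximum weeks at end of Month 8 |
|---|---|---|
| 1 | 12.86 + 8 × 4.348 | 47.6 |
| 2 | 12.86 + 7 × 4.348 | 43.3 |
| 3 | 12.86 + 6 × 4.348 | 38.9 |
| 4 | 12.86 + 5 × 4.348 | 34.6 |

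Counting actual days with February as Month 1 also gives 34.6 weeks for the first day of Month 4. It gives 30.3 weeks for the last day. A woman who entered at 8 weeks (assumed) would be at 25.4 to 29.7 weeks. Month 3 enrollees at the upper limit of gestation are at 34.7 to 38.9 weeks, so some of them will also be undelivered.

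**Gestation at the antepartum survey.** At the end of Month 7, Month 4 enrollees are at most 12.86 + 4 × 4.348 = about 30.2 weeks. For most pregnancies that is not the last visit before delivery.

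**Early-onset preeclampsia.** The protocol gives no gestational cut-off. If 34 weeks is assumed, the margin in the best case is 34.6 − 34 = 0.6 weeks, about 4 days. Only women at the upper limit of gestation who enrol in the first few days of Month 4 would be observed to that point.

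**When the last women would finish.** Take enrolment at the end of Month 4, delivery at 40 weeks and a 6-week postpartum window (assumed; the protocol fixes none), with 6/4.348 = 1.38 months:

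- Entry at 12 weeks 6 days: (40 − 12.86)/4.348 = 6.24 months. 4 + 6.24 + 1.38 = 11.62 months elapsed, i.e. during Month 12.
- Entry at 8 weeks: (40 − 8)/4.348 = 7.36 months. 4 + 7.36 + 1.38 = 12.74 months elapsed, i.e. during Month 13.
- Entry at 6 weeks: (40 − 6)/4.348 = 7.82 months. 4 + 7.82 + 1.38 = 13.20 months elapsed, i.e. during Month 14.

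**The case against.** The best defence is that the table is a planning aid and that the governing text is already right. The Synopsis follows women to the postpartum survey, section III.G ties the antepartum payment to the last visit before delivery, and Appendix E ties collection to pregnancy stage. On that view staff would simply continue past Month 8. This stands in part: much of the remedy is already in the protocol, and the defect is an internal inconsistency. But the table is the only schedule, it names the data export and the end of the study, and no other text overrides it.

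A second defence is that the listed key outcomes (blood pressure, blood pressure monitoring, aspirin compliance, feasibility) largely accrue during pregnancy. That is also fair, and it limits the damage to Aims 2 and 3 and to acceptability measured postpartum.

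A reader might infer more than the documents support:

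- *That delivery, preeclampsia and postpartum outcomes cannot exist for these women.* Preeclampsia before closure is observable, some pregnancies end early, and the hypothesis concerns early-onset disease.
- *That late-pregnancy blood pressure is unobserved.* Intervention-arm logs run throughout participation and records are abstracted on an ongoing basis, so readings can extend to closure.
- *That half of each arm is lost.* The table does not split Month 4 enrolment by arm, and its 36 per group conflicts with 2:1 allocation.
- *That the whole data set is selected on preeclampsia.* Only delivery and postpartum data depend on the pregnancy having ended, and early delivery is not the same as preeclampsia.
- *That no Month 3 enrollee could finish.* At up to 38.9 weeks some will have delivered.

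**Conclusion.** The contradiction is real, and the protocol should not stand as written. At least 50% of the sample (up to 72%, depending on how the enrolment counts are reconciled) is at no more than 34.6 weeks when the study concludes. That ceiling uses only the protocol's own entry limit and calendar, and it is a best case.

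The consequence is truncated follow-up. For nearly all Month 4 enrollees, term delivery, later-onset preeclampsia and the postpartum survey will be missing. Early-onset preeclampsia will be partly truncated; how far depends on a cut-off that the protocol does not state. Any delivery or postpartum data from this group will come only from pregnancies that ended before about 35 weeks, so those data cannot be read as representative of it. The required closing date, unlike the 34.6-week ceiling, rests on assumptions: 8 weeks to 12 weeks 6 days at entry, delivery at 40 weeks and a 6-week postpartum window.

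**What to change.** Reconcile the timeline table with the Synopsis, section III.G and Appendix E:

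1. Replace the fixed Month 8 conclusion with a data lock after the last randomised woman has delivered and her postpartum survey window has ended. State the length of that window. If enrolment ends in Month 4, this is about Month 12 to 13 on the assumptions above, and Month 14 if some women enter as early as 6 weeks.
2. In the table, tie the antepartum and postpartum collections to each woman's pregnancy stage or delivery date instead of Months 7 and 8.
3. Correct the enrolment counts so that they sum to the stated total.

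Keeping Month 8 and reporting delivery and postpartum outcomes only for early enrollees is not workable. Even at 12 weeks 6 days, reaching 40 weeks plus a 6-week window takes 6.24 + 1.38 = 7.62 months. A woman would have to enrol within the first 8 − 7.62 = 0.38 months, before the middle of Month 1, and the table enrols only 10 women in the whole of that month.

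The cost is a protocol amendment, about 4 to 5 more months of survey, log and health-record collection, and a later read-out. The added months need continued staff effort because the logs run throughout participation. No extra participants or procedures are needed.
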